- g Tumor assessments must be done according to Response Evaluation Criteria in Solid Tumors (RECIST) Version 1.1 (see [Appendix B](#)) and should include computed tomography (CT) scans or magnetic resonance imaging (MRI) of **the chest and abdominopelvic cavity** at screening and, if clinically indicated, imaging of any other known or suspected sites of disease (e.g., brain) using an appropriate method (CT scan or MRI). If there is a history or suspicion of CNS metastasis a CT scan of the head or MRI of the brain must be performed. The same radiographic procedure must be used throughout the study. In case of suspected (but not otherwise confirmed) bone metastasis at screening or in subsequent cycles, tumor assessment should include a bone scan. CT scans or MRI of **the abdominopelvic cavity** (and chest ONLY if the screening imaging documented sites of disease in the chest) and correlative imaging should then be repeated at each tumor assessment. Assessments will be performed by the Investigator at screening and every 6 weeks ( $\pm 7$  days) during the first 36 weeks, and then every 9 weeks ( $\pm 7$  days), taking as reference the first dose date for non-randomized patients and randomization date for randomized patients. Thereafter, patients will be evaluated at the EOT visit by CT scans or MRI of **the chest and abdominopelvic cavity**, and as clinically indicated, until PD as per RECIST Version 1.1 as assessed by the Investigator, initiation of new anti-cancer treatment, unacceptable toxicity, death, lost to follow up, or withdraw of consent from any further participation and at the discretion of the Investigator. Baseline tumor assessments must be performed within 28 days before first administration of study drug for non-randomized patients and must be before randomization date for randomized patients. Tumor assessments should occur regardless of dose interruptions/delays. Additionally, all images including CT and MRI may be submitted to a central imaging vendor for independent retrospective review (Section 7.3).

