- q 30-day safety follow-up will be performed for at least 30 days after the last study drug administration or before starting new anti-cancer treatment, whichever comes first, as described in Section 7.4.2. If the day of treatment discontinuation is over 30 days from last study drug administration, this follow up visit is not needed.
- r Patients who did not experience progressive disease or death during the 30-day safety follow-up will be followed until the start of a new anti-cancer treatment, progressive disease, death, lost to follow up, withdrawal of consent from any further participation, or at the discretion of the Investigator. Tumor assessment per RECIST v1.1 will be performed at the same frequency as for patients receiving treatment depending on when the discontinuation occurs (i.e., every 6 weeks [ $\pm 7$  days] for the first 36 weeks and, every 9 weeks [ $\pm 7$  days] thereafter). If a new anticancer therapy is planned to start before the next planned tumor assessment, the tumor assessment may be performed just before starting the new therapy.
- s If patient provides consent, samples should be collected prior to study drug infusion. Starting at Cycle 5, Day 1, every 4 cycles thereafter (Cycle 9, Cycle 13, etc.), and at the EOT visit. For patients with suspected or confirmed COVID-19 infections, follow the dose modifications in [Appendix H](#).
- t A washout period of no less than 14 days is required before restarting DS-6157.

*CONFIDENTIAL*

Study Drug: DS-6157a

Sponsor/Innovations Study Numbers: DS6157-A-U101/GI 289

Final Protocol: 17 August 2021 Version 6.0

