## 6. DOSE MODIFICATIONS

If toxicity occurs, the toxicity will be graded using the NCI [CTCAE Version 5.0](#), and appropriate supportive care treatment will be administered to decrease the signs and symptoms thereof. Dose adjustments will be based on the organ system exhibiting the greatest degree of toxicity.

The Investigator will evaluate which toxicities are attributed to the study drug and adjust the dose of the drug as recommended below. All dose modifications must be based on the worst preceding toxicity (CTCAE version 5.0).

Specific criteria for interruption, re-initiation, dose reduction, and/or discontinuation of DS-6157a are listed in [Table 2](#). All interruptions or modifications must be recorded on the AE and drug administration CRFs. Appropriate clinical experts must be consulted as deemed necessary.

There will be no dose modifications for Grade 1 or Grade 2 AEs unless specified below in [Table 2](#). For a recurrent Grade  $\geq 3$  AE, the patient will be permanently discontinued from study treatment based on Investigator discretion.

Prophylactic or supportive treatment for expected toxicities, including management of TEAEs, will be at the treating physician's discretion and per institutional guidelines, except for prophylactic treatment prior to the DLT evaluation period.

*CONFIDENTIAL*

Two dose reductions will be permitted (the dose cannot be reduced to <1.6 mg/kg) in any patient. Once the dose of DS-6157a has been reduced because of toxicity, all subsequent cycles must be administered at that lower dose level unless further dose reduction is required. More than 2 dose reductions are not allowed and the patient will be withdrawn from the study treatment if further toxicity meeting the requirement for dose reduction occurs.

During the dose escalation part of the trial, intra-patient dose escalation (IPDE) of DS-6157a may be allowed on a case by case basis in patients who may benefit from IPDE based on the clinical judgement of the investigator and in agreement with the Medical Monitor and Sponsor. The eligibility criteria for consideration of patients for IPDE are the following:

- Patient must provide consent for IPDE.
- A minimum of 4 cycles of treatment and evaluations must be completed before IPDE
- Patient must meet inclusion criteria of #1-3, 6 and 8 based on the most recent data, and 9 (except for DS-6157 treatment) again. Any criteria that did not meet the eligibility can be re-tested.

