- Patient who meets any of exclusion criteria based on the most recent data, or who experienced ILD of any grade or any other dose modification toxicity event during DS-6157a treatment will not be eligible for IPDE.

IPDE may be conducted up to a dose that is 1 dose level below the dose already established to be safe and tolerable. Dose escalation should not be more than 3 dose levels at a time. The actual dose level will be decided based on the overall individual clinical status and PK profile. A patient may be allowed further IPDE after completing a minimum of another 4 cycles after the first IPDE, as long as the conditions for IPDE are met. AEs arising after IPDE should follow dose modifications/reductions per [Table 2](#), but further re-escalations will be prohibited after such events.

Dose can be delayed for up to 28 days from the planned date of administration. If a patient has a persisting AE/SAE that requires a longer dose delay, then patient will be withdrawn from the study after consulting with Medical Monitor.

Treatment cycles for a patient for whom DS-6157a dosing was temporarily withheld for any reason may have future cycles scheduled based on the date of the last DS-6157a dose. However, the tumor assessments will follow the pre-specified schedules relative to the start of the study treatment (Cycle 1 Day 1).

Investigators may contact the Medical Monitor or designee to discuss questions regarding dose modification or discontinuation of study drug.

All confirmed or suspected coronavirus disease 2019 (COVID-19) infection events must be recorded in the eCRF. Please refer to [Appendix H](#) for additional information on dose modifications.

*CONFIDENTIAL*

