	
Evaluations should include:
 
 
• high resolution CT
 
• pulmonologist consultation (infectious Disease consultation as clinically indicated)
 
• blood culture and CBC. Other blood tests could be considered as needed
 
• Consider bronchoscopy and bronchoalveolar lavage if clinically indicated and feasible.
 
• pulmonary function tests and pulse oximetry (SpO2)
 
• arterial blood gases if clinically indicated
 
• one blood sample collection for PK and exploratory biomarker analysis as soon as ILD/pneumonitis is suspected, if feasible.
 
 
Other tests could be considered, as needed.
 
If the AE is confirmed to be ILD/pneumonitis, follow the management guidance as outlined below.
 
All events of ILD/pneumonitis regardless of severity or seriousness will be followed until resolution including after drug discontinuation.

Grade 1	
The administration of DS-6157a must be interrupted for any ILD/pneumonitis events regardless of grade.
 
 
• Monitor and closely follow-up in 2 to 7 days for onset of clinical symptoms and pulse oximetry
 
• Consider follow-up imaging in 1-2 weeks (or as clinically indicated).
 
• Consider starting systemic steroids (e.g. at least 0.5 mg/kg/day prednisone or equivalent) until improvement, followed by gradual taper over at least 4 weeks.
 
• If worsening of diagnostic observations despite initiation of corticosteroids, then follow Grade 2 guidelines.*
 
 
For Grade 1 events, DS-6157a can be restarted only if the event is fully resolved to Grade 0:
 
 
- If resolved in ≤28 days from day of onset, maintain dose
 
- If resolved in >28 days from day of onset, reduce dose
 

	
1 level
 
However, if the event Grade 1 ILD occurs beyond cycle Day 22 and has not resolved within 49 days from the last infusion, the drug should be discontinued.
 
* If patient is asymptomatic, then patient should still be considered as Grade 1 even if steroid treatment is given.

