### 7.3 Tumor Assessments During Study Treatment

Patient will remain on treatment as long as, in the opinion of the Investigator, they are deriving benefit and the criteria for withdrawal listed in Section 3.3 are not met. Please refer to the [Assessment Schedule](#) for detailed outlines of each visit during the treatment period for each part of the study.

Response will be assessed by CT scans or MRI of **the abdominopelvic cavity** (and chest ONLY if the screening imaging documented sites of disease in the chest) at 6-week intervals ( $\pm 7$  days) during the first 36 weeks and every 9 weeks ( $\pm 7$  days) thereafter, taking as reference the first dose date for non-randomized patients and the randomization date for randomized patients. Then, patients will be assessed at the EOT visit by CT scans or MRI of **the chest and**

*CONFIDENTIAL*

**abdominopelvic cavity**, and at the discretion of the Investigator. Patients will continue treatment with DS-6157a, until progression of disease (PD) according to RECIST Version 1.1 as assessed by the Investigator, initiation of new anti-cancer treatment, unacceptable toxicity, death, lost to follow up, or withdrawal of consent. However, patients may be treated beyond initial radiological progression (according to RECIST Version 1.1) on a case-by-case basis (with agreement from the Medical Monitor), if the Investigator feels that it is in the patient's best interest, the patient re-consents to continue receiving study treatment in a separate consent form, and as long as the patient is deriving benefit from the treatment, and no other criterion listed in Section 3.3 is fulfilled.

The assessments to be performed at this time are specified in [Appendix B](#) and will occur regardless of dose interruptions/delays. Please refer to Section 9 for further instructions on evaluating response (e.g., PD, SD).

The following assessments will be performed if abnormal at baseline or if clinically indicated:

- CT scan or MRI of the chest, abdomen, and pelvis/lower abdomen
- CT scan of the head/MRI of the brain if history of CNS metastasis
- Bone scan in case of suspected (but not confirmed) bone metastasis

Additionally, all images including CT and MRI may be submitted to a central imaging vendor for independent retrospective review.

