## **7.4 Follow-up Periods and Study Completion**

### **7.4.1 End-of-Treatment Visit**

The end-of-treatment (EOT) visit will be performed after the Investigator decides with the patient to permanently discontinue the study treatment for any reason, as soon as possible but within 30 days of the last dose of treatment or before the patient starts another therapy, whichever occurs sooner.

The assessments of the EOT visit will then be performed instead of the next planned visit. If the patient discontinues treatment without having PD, the patient will be followed until the start of the next anti-cancer therapy, PD, death, lost to follow-up, withdrawn consent, or end of study, whichever occurs sooner.

*CONFIDENTIAL*

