#### 7.4.3 Long-term Follow-up

Patients who did not experience progressive disease or death during the 30-day safety follow-up will be followed until the start of a new anti-cancer treatment, progressive disease, death, lost to follow up, withdrawal of consent, or at the discretion of the Investigator. Tumor assessment will be performed per RECIST v1.1 at the same frequency specified in Section 7.3 (i.e., every 6 weeks [ $\pm 7$  days] for the first 36 weeks and, every 9 weeks [ $\pm 7$  days] thereafter). If a new anticancer therapy is planned to start before the next planned tumor assessment, the tumor assessment may be performed just before starting the new therapy.

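### Section 6 takes a patient with a long AE-related dose delay off the study, while the parallel limits stop treatment only and Section 7.4 continues the scans

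*Combined protocol and SAP*

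**What the plan says.** Section 6 allows a dose to be delayed by up to 28 days from its planned date. If a persisting AE or SAE needs longer, the "patient will be withdrawn from the study after consulting with Medical Monitor".

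The neighbouring limits are worded differently. For a patient who has used both permitted dose reductions, Section 6 says "the patient will be withdrawn from the study treatment if further toxicity meeting the requirement for dose reduction occurs". In Table 2, if Grade 1 ILD arising beyond cycle Day 22 "has not resolved within 49 days from the last infusion, the drug should be discontinued".

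Follow-up after treatment is set out elsewhere. Section 7.4.1 says: "If the patient discontinues treatment without having PD, the patient will be followed until the start of the next anti-cancer therapy", with progression, death, loss to follow-up, withdrawn consent and end of study as the other end points. Section 7.4.3 ends long-term follow-up at "start of a new anti-cancer treatment, progressive disease, death, lost to follow up, withdrawal of consent, or at the discretion of the Investigator". Footnote r of the Assessment Schedule adds: "Tumor assessment per RECIST v1.1 will be performed at the same frequency as for patients receiving treatment depending on when the discontinuation occurs". None of these lists an AE or a long dose delay as a reason to stop scanning.

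**The concern.** The Section 6 sentence sends one group of patients off the study at a point where the rest of the protocol would take them off the drug and keep scanning them. Those patients have by definition a persisting AE or SAE, whether or not it is drug-related, so the reason their scans end may be related to prognosis.

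PFS, DoR and ORR are listed under the primary objective in Dose Expansion (Table 1). Section 10.5.2 censors PFS and DoR at the last adequate tumour assessment when no event is recorded, and it counts CR or PR only if confirmed at least 4 weeks later. Stopping scans therefore affects three descriptions: PFS, DoR and, for a response not yet confirmed, ORR. No analysis rule written later can recover scans that were not taken.

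**Working it through.** **1. The delay limit.** The cycle is 21 days (Section 7.1) and the maximum delay is 28 days from the planned date (Section 6). With the previous dose given on schedule, the limit falls at 21 + 28 = 49 days after the last dose. That reproduces the 49 days from last infusion in the Grade 1 ILD row of Table 2. The same time limit therefore has two different consequences.

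**2. The limits side by side.**

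| Trigger | Place | What ends |
|---|---|---|
| AE/SAE needing more than 28 days' delay | Section 6 | the study |
| Toxicity calling for a third dose reduction | Section 6 | study treatment |
| Recurrent Grade ≥3 AE | Section 6 | study treatment, at Investigator discretion |
| Grade 1 ILD unresolved at 49 days | Table 2 | the drug |
| Grade 4 ocular, creatinine or AST/ALT toxicity | Table 2 | study treatment |
| Grade 4 COVID-19 | Appendix H, Table 4 | study drug |

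Only the first row ends study participation.

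**3. Whether the two terms differ in this plan.** They do. Section 10.5.1 summarises discontinuation of study treatment and discontinuation from the study separately. Section 10.2 sets the primary-analysis cut-off once every patient has either left the study or been followed for 6 months, so a patient labelled as off study satisfies the cut-off without 6 months of follow-up.

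**4. What follows if the sentence is obeyed.**
- PFS and DoR: no further scans, so a patient without an event is censored at the last adequate assessment (Section 10.5.2).
- Confirmation of response: one more scan is likely, since Section 7.3 says "Then, patients will be assessed at the EOT visit by CT scans or MRI of" the chest and abdominopelvic cavity. Let a response be first seen on day r and the EOT scan be on day e, both counted from the last dose. Confirmation needs e − r ≥ 28. If e = 49, r must be 21 or less. If e = 30, the outer limit of the EOT window in Section 7.4.1, r must be 2 or less. The protocol does not fix e for this route, so the number of responses at risk cannot be derived.
- AE follow-up: not lost. Section 11.2.2 still requires AEs that lead to study discontinuation to be followed. The gap is in tumour follow-up.

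**5. Size.** The protocol gives no expected frequency of AE delays beyond 28 days, so the effect cannot be computed from it. For scale only, a simulation was run in which every input is an assumption:
- 30 patients, 3,000 runs per setting, exponential PFS with median 3 or 6 months;
- 1, 2, 3 or 5 patients withdrawn between 1.4 and 6 months;
- progression hazard after withdrawal 1, 2 or 3 times that before.

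The figures below are censoring at withdrawal minus continued follow-up.

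| Withdrawn | 6-month PFS rate (percentage points) | Median PFS, true 3 months | Median PFS, true 6 months |
|---|---|---|---|
| 1 to 3 of 30 | −0.5 to +2.8 | +0.03 to +0.13 months | +0.14 to +0.69 months |
| 5 of 30, hazard ratio 3 | +4.1 to +4.5 | +0.19 months | +0.81 months |

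Part of the shift in the median is a small-sample feature of the Kaplan-Meier median. With 1 to 3 withdrawn and a hazard ratio of 1, it is already 0.03 to 0.06 months (true median 3) or 0.14 to 0.26 months (true median 6). For comparison, Table 3 of the protocol gives an exact 95% interval of 19.9% to 56.1% for 11 of 30, a width of 56.1 − 19.9 = 36.2 points.

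**The case against.** The strongest reply is that, in context, the sentence can only mean study treatment. Section 6 is about interrupting, reducing and stopping the drug. Section 3.3 lists an adverse event among reasons to leave study treatment, and it speaks loosely of staying on study when it means staying on the drug. Section 7.4.4, although titled as patient withdrawal, describes patients who stop study treatment. Footnote q already covers a stop decided more than 30 days after the last dose and waives only the 30-day visit. A patient on this route has stopped treatment without progression, so Section 7.4.1 applies on its own terms, and the Medical Monitor has to be consulted first.

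Most of this stands. It makes a slip the likely explanation, and it makes the harm conditional on a site acting on the sentence despite Section 7.4. It does not remove the instruction. Section 3.3 is permissive and silent on scans, and the consultation requirement does not say that follow-up continues.

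It also stands that the conflict is with a default. Section 7.4.3 and footnote r let follow-up end at the Investigator's discretion, so some censoring of this kind can occur under either wording.

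Two stronger readings are tempting and not supported:
- A reader might take footnote g as a second contradiction, because it lists "initiation of new anti-cancer treatment, unacceptable toxicity, death, lost to follow up, or withdraw of consent from any further participation" as ends of tumour evaluation. Section 7.3 uses nearly the same list for when treatment ends, so footnote g reads naturally as on-treatment imaging, and footnote r governs scans afterwards.
- A reader might count, cycle by cycle, which patients would lose a confirmatory scan. Any such count rests on one assumed EOT date and changes with it, as the comparison of day 49 with day 30 shows.

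**Conclusion.** The inconsistency is real, in current text, and minor. One sentence in Section 6 ends study participation where every parallel limit ends treatment, and it conflicts with the default tumour follow-up in Section 7.4. It is probably a drafting slip.

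If followed, it ends scans before progression, censors PFS and DoR for an AE-related and possibly informative reason, may leave a response unconfirmed, and labels the patient as off study for the primary-analysis cut-off. That is conditional on three things: an AE delay beyond 28 days, no progression yet, and a site acting on the wording. The documents give no frequency for any of them.

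A reader might infer that the plan intends to drop these patients from follow-up, or that PFS is materially biased. Neither is supported. Section 7.4 points the other way on intent, and the size cannot be established from the documents. The number affected is probably small, which is a judgement. On assumed inputs, the shift with 1 to 3 of 30 patients affected is small against the uncertainty in a cohort of 30. Section 10.2 plans no statistical testing, so the consequence is a less reliable description and not a wrong test decision.

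**What to change.** In Section 6, replace the words *withdrawn from the study* with *permanently discontinued from study treatment and followed per Section 7.4*, and keep the consultation with the Medical Monitor. No change to footnote g is needed.

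The cost is one phrase at the next amendment, with the IRB/IEC approval that Section 14.1 requires of any amendment. It adds no visits or scans beyond those already in Section 7.4.3 and footnote r. Because the Investigator-discretion clause stays, the change restores the default follow-up and does not guarantee that every scan is done.

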**Table 2 Dose Modifications for DS-6157a**

Worst toxicity CTCAE v5.0 Grade (unless otherwise specified)	Dose or schedule modification for DS-6157a
No toxicity	Maintain dose and schedule
Infusion-Related Reaction	
Grade 1 (Mild transient reaction; infusion interruption not indicated; intervention not indicated)	No interruption or change in the infusion rate is indicated.
Grade 2 (Therapy or infusion interruption indicated but responds promptly to symptomatic treatment (e.g., antihistamines, nonsteroidal anti-inflammatory drugs (NSAIDs), narcotics, IV fluids); prophylactic medications indicated for ≤24 hrs)	
Grade 2 IRR occurring during infusion of DS-6157a:
 
 
Administration of DS-6157a must be interrupted and symptomatic treatment started (e.g. antihistamines, NSAIDs, narcotics, IV fluids).
 
If the event resolves or improves to Grade 1, infusion can be re-started at a 50% reduced infusion rate.
 
 
Grade 2 IRR occurring post infusion of DS-6157a:
 
 
Symptomatic treatment must be started (e.g., antihistamines, antiemetics, NSAIDs, IV fluids) until the event resolves or improves to Grade 1.
 
 
Subsequent administrations of DS-6157a after any Grade 2 IRR occurring during or post infusion of DS-6157a :
 
 
Premedication (e.g., acetaminophen, diphenhydramine, and/or corticosteroids or equivalents) should be considered at the Investigator’s discretion. If the Grade 2 event recurs despite pre-medication, then all subsequent administrations of DS-6157a must be conducted at the 50% reduced infusion rate and/or with pre-medication.
 
If the infusion rate is reduced by 50% (regardless of pre-medication) and the Grade 2 event does not recur at a given cycle, then administrations of DS-6157a at subsequent cycles can be conducted at the initial infusion rate at the investigator’s discretion. If the Grade 2 event recurs at the initial infusion rate, then all subsequent administrations of DS-6157a must be conducted at the 50% reduced infusion rate and with pre-medication.
 

Grade 3 or 4 (Prolonged or life-threatening consequences, urgent intervention indicated)	Administration of DS-6157a must be discontinued immediately and permanently.  Urgent intervention indicated. Antihistamines, steroids, epinephrine, bronchodilators, vasopressors, intravenous fluid therapy, oxygen inhalation etc., must be administered.
Hematologic Toxicity	
Neutrophil Count Decreased and/or White Blood Cell Count Decreased	
Grade 3	Delay dose until resolved to $\leq$ Grade 2, then maintain dose
Grade 4	Delay dose until resolved to $\leq$ Grade 2, Reduce dose by 1 level
Febrile Neutropenia (Absolute neutrophil count $<1 \times 10^9/L$ , fever $>38.3^\circ C$ or a sustained temperature of $\geq 38^\circ C$ for more than one hour)	Delay dose until resolved, Reduce dose by 1 level
Lymphocyte Count Decreaseda	
Grade 1 to Grade 3	No dose modification
Grade 4 ( $<0.2 \times 10^9/L$ )	Delay dose until resolved to $\leq$ Grade 2: - If resolved in $\leq 14$ days from day of onset, maintain dose - If resolved in $>14$ days from day of onset, reduce dose 1 level
Anemia	
Grade 3 (Hemoglobin (Hb) $<8.0$ g/dL); transfusion indicated	Delay dose until resolved to $\leq$ Grade 2, then maintain dose
Grade 4 Life threatening consequences; urgent intervention indicated	Delay dose until resolved to $\leq$ Grade 2, then reduce dose 1 level
Platelet Count Decreased	
Grade 3 (Platelets $<50 - 25 \times 10^9/L$ )	Delay dose until resolved to $\leq$ Grade 1: - If resolved in $\leq 7$ days from day of onset, maintain dose - If resolved in $>7$ days from day of onset, reduce dose 1 level
Grade 4 (Platelets $<25 \times 10^9/L$ )	Delay dose until resolved to $\leq$ Grade 1, then reduce dose 1 level
Cardiac Toxicity	
Symptomatic congestive heart failure (CHF)	Discontinue patient from study treatment

CONFIDENTIAL

Sponsor/Innovations Study Numbers: DS6157-A-U101/GI 289

Decrease in left ventricle ejection fraction (LVEF) 10-20% (absolute value), but LVEF >45%	Continue treatment with DS-6157a
LVEF 40% to 45% and decrease is <10% (absolute value) from baseline	Continue treatment with DS-6157a Repeat LVEF assessment within 3 weeks
LVEF 40% to 45% and decrease is 10% - 20% (absolute value) from baseline	Interrupt DS-6157a dosing Repeat LVEF assessment within 3 weeks If LVEF has not recovered to within 10% (absolute value) from baseline, discontinue patient from study treatment. If LVEF recovers to within 10% from baseline, resume treatment with study drug.
LVEF <40% or >20% (absolute value) drop from baseline	Permanently discontinue from study treatment
Electrocardiogram QT prolonged	
Grade 3 (Average QTcF >500 ms or >60 ms change from baseline)	Repeat the ECG in triplicate within 1 hour and then monitor at the frequency determined by the Investigator's discretion. Delay dose until resolved to ≤ Grade 1 (QTcF ≤480 ms or change from baseline ≤30 msec), determine if another medication the patient was taking may be responsible and can be adjusted or if there are any changes in serum electrolytes that can be corrected, then if attributed to DS-6157a and confirmed on repeat ECG triplicate, reduce dose 1 level.
Grade 4 (Torsade de pointes or polymorphic ventricular tachycardia or signs/symptoms of serious arrhythmia)	Discontinue patient from study treatment
Interstitial lung disease (ILD)/pneumonitis	If a patient develops radiologic changes potentially consistent with ILD/pneumonitis or an acute onset of new or worsening pulmonary function or other related signs/symptoms such as dyspnea, cough, or fever, rule out ILD/pneumonitis.  If the AE is confirmed to have an etiology other than ILD/pneumonitis, follow the management guidance outlined in the "Other Non-Laboratory Adverse Events" dose modification section below.  If the AE is suspected to be ILD/pneumonitis, treatment with study drug should be interrupted pending further evaluations.

CONFIDENTIAL

	
Evaluations should include:
 
 
• high resolution CT
 
• pulmonologist consultation (infectious Disease consultation as clinically indicated)
 
• blood culture and CBC. Other blood tests could be considered as needed
 
• Consider bronchoscopy and bronchoalveolar lavage if clinically indicated and feasible.
 
• pulmonary function tests and pulse oximetry (SpO2)
 
• arterial blood gases if clinically indicated
 
• one blood sample collection for PK and exploratory biomarker analysis as soon as ILD/pneumonitis is suspected, if feasible.
 
 
Other tests could be considered, as needed.
 
If the AE is confirmed to be ILD/pneumonitis, follow the management guidance as outlined below.
 
All events of ILD/pneumonitis regardless of severity or seriousness will be followed until resolution including after drug discontinuation.

Grade 1	
The administration of DS-6157a must be interrupted for any ILD/pneumonitis events regardless of grade.
 
 
• Monitor and closely follow-up in 2 to 7 days for onset of clinical symptoms and pulse oximetry
 
• Consider follow-up imaging in 1-2 weeks (or as clinically indicated).
 
• Consider starting systemic steroids (e.g. at least 0.5 mg/kg/day prednisone or equivalent) until improvement, followed by gradual taper over at least 4 weeks.
 
• If worsening of diagnostic observations despite initiation of corticosteroids, then follow Grade 2 guidelines.*
 
 
For Grade 1 events, DS-6157a can be restarted only if the event is fully resolved to Grade 0:
 
 
- If resolved in ≤28 days from day of onset, maintain dose
 
- If resolved in >28 days from day of onset, reduce dose
 

	
1 level
 
However, if the event Grade 1 ILD occurs beyond cycle Day 22 and has not resolved within 49 days from the last infusion, the drug should be discontinued.
 
* If patient is asymptomatic, then patient should still be considered as Grade 1 even if steroid treatment is given.

Grade 2	
Permanently discontinue patient from study treatment.
 
 
• Promptly start and treat with systemic steroids (e.g., at least 1mg/kg/day prednisone or equivalent) for at least 14 days or until complete resolution of clinical and chest CT findings, then followed by a gradual taper over at least 4 weeks.
 
• Monitor symptoms closely.
 
• Re-image as clinically indicated.
 
• If worsening or no improvement in clinical or diagnostic observations in 5 days,             
 
• Consider increasing dose of steroids (e.g., 2 mg/kg/day prednisone or equivalent) and administration may be switched to intravenous (e.g. methylprednisolone).
 
• Re-consider additional work-up for alternative etiologies as described above.
 
• Escalate care as clinically indicated.
 
 
 

Grade 3 or 4	
Permanently discontinue patient from study treatment.
 
 
• Hospitalization required.
 
• Promptly initiate empiric high-dose methylprednisolone IV treatment (e.g., 500-1000 mg/day for 3 days), followed by at least 1.0 mg/kg/day of prednisone (or equivalent) for at least 14 days or until complete resolution of clinical and chest CT findings, then followed by a gradual taper over at least 4 weeks.
 
• Re-image as clinically indicated.
 
• If still no improvement within 3 to 5 days,
 

*CONFIDENTIAL*

Sponsor/Innovations Study Numbers: DS6157-A-U101/GI 289

	
 
Re-consider additional work-up for alternative etiologies as described above.
 
 
Consider other immuno-suppressants and/or treat per local practice.

Ocular Toxicity	
Grade 3	
Delay dose until resolved to <math>\leq</math>Grade 1:            If resolved in <math>\leq 7</math> days from day of onset, maintain dose            If resolved in <math>>7</math> days from day of onset, reduce dose 1 level

Grade 4	Discontinue patient from study treatment
Blood creatinine increased	
Grade 3 ( $>3.0 \times$ baseline or $>3.0$ to $6.0 \times$ upper limit of normal [ULN])	Delay dose until resolved to $\leq$ Grade 1 or baseline, then reduce dose 1 level
Grade 4 ( $>6.0 \times$ ULN)	Discontinue patient from study treatment
Hepatic Toxicity	
Aspartate aminotransferase (AST) or alanine aminotransferase (ALT) with simultaneous total bilirubin (TBL)	
AST/ALT $\geq 3.0 \times$ ULN with simultaneous TBL $>2.0 \times$ ULN	
Delay study medication until drug-induced liver injury can be ruled out.
 
If drug-induced liver injury is ruled out, the patient should be treated accordingly, and resumption of study drug may occur after discussion between the Investigator and Sponsor.
 
If drug-induced liver injury cannot be ruled out from diagnostic workup, permanently discontinue study treatment.
 
Monitor AST/ALT and TBL twice weekly until resolution or return to baseline.

Aspartate aminotransferase (AST) or alanine aminotransferase (ALT)	
Grade 2 ( $>3.0 - 5.0 \times$ ULN if baseline was normal; $>3.0 - 5.0 \times$ baseline if baseline was abnormal)	No action for Grade 2 AST/ALT

Grade 3 (<math>>5.0 - 20.0 \times</math> ULN if baseline was normal; <math>>5.0 - 20.0 \times</math> baseline if baseline was abnormal)
 
In patients without liver metastases and patients with liver metastases and
	
Repeat testing within 3 days. Delay dose until resolved to <math>\leq</math> Grade 1 if baseline <math>\leq 3 \times</math> ULN, otherwise delay dose until resolved to <math>\leq</math> baseline, then:
 
If resolved in <math>\leq 7</math> days from day of onset, maintain dose            If resolved in <math>>7</math> days from day of onset, reduce dose 1

CONFIDENTIAL

baseline level $\leq 3 \times \text{ULN}$	level
Grade 3 ( $>8.0 - 20.0 \times \text{ULN}$ if baseline was normal; $>8.0 - 20.0 \times \text{baseline}$ if baseline was abnormal)  In patients with liver metastases, if the baseline level was $>3 \times \text{ULN}$	Repeat testing within 3 days. Delay dose until resolved to $\leq$ baseline level, then: If resolved in $\leq 7$ days from day of onset, maintain dose If resolved in $>7$ days from day of onset, reduce dose 1 level
Grade 4 ( $>20.0 \times \text{ULN}$ if baseline was normal; $>20.0 \times \text{baseline}$ if baseline was abnormal)	Discontinue patient from study treatment
Total Bilirubin	
Grade 2 ( $>1.5 - 3.0 \times \text{ULN}$ if baseline was normal; $>1.5 - 3.0 \times \text{baseline}$ if baseline was abnormal)	If no documented Gilbert's syndrome or liver metastases at baseline, delay dose until resolved to $\leq$ Grade 1: 
 
- If resolved in <math>\leq 7</math> days from day of onset, maintain dose
 
- If resolved in <math>>7</math> days from day of onset, reduce dose 1 level
 
 If documented Gilbert's syndrome or liver metastases at baseline, continue study treatment
Grade 3 ( $>3.0 - 10.0 \times \text{ULN}$ if baseline was normal; $>3.0 - 10.0 \times \text{baseline}$ if baseline was abnormal)	If no documented Gilbert's syndrome or liver metastases at baseline, repeat testing within 3 days. Delay dose until resolved to $\leq$ Grade 1: 
 
- If resolved in <math>\leq 7</math> days from day of onset, reduce dose 1 level
 
- If resolved in <math>>7</math> days from day of onset, discontinue DS-6157a
 
 If documented Gilbert's syndrome or liver metastases at baseline, repeat testing within 3 days. Delay dose until resolved to $\leq$ Grade 2: 
 
- If resolved in <math>\leq 7</math> days from day of onset, reduce dose 1 level
 
- If resolved in <math>>7</math> days from day of onset, discontinue DS-6157a
 

Grade 4 ( $>10.0 \times \text{ULN}$ if baseline was normal; $>10.0 \times \text{baseline}$ if baseline was abnormal)	Discontinue patient from study treatment
Blood Alkaline Phosphatase Increased	
Grade 3 ( $>5.0 - 20.0 \times \text{ULN}$ if baseline was normal; $>5.0 - 20.0 \times \text{baseline}$ if baseline was abnormal)  or	No modification unless determined by the Investigator to be clinically significant or life-threatening.

CONFIDENTIAL

Grade 4 (>20.0 × ULN if baseline was normal; >20.0 × baseline if baseline was abnormal)	
Gastrointestinal	
Nausea	
Grade 3	Delay dose until resolved to ≤ Grade 1 If resolved in ≤7 days from day of onset, maintain dose If resolved in >7 days from day of onset, reduce dose 1 level
Vomiting	
Grade 3	Delay dose until resolved to ≤ Grade 1 If resolved in ≤7 days from day of onset, maintain dose If resolved in >7 days from day of onset, reduce dose 1 level
Grade 4	Discontinue patient from study treatment
Diarrhea/Colitis	
Grade 3	Delay dose until resolved to ≤ Grade 1 If resolved in ≤3 days from day of onset, maintain dose If resolved in >3 days from day of onset, reduce dose 1 level
Grade 4	Discontinue patient from study treatment
Other Laboratory Adverse Events	
Grade 3	Delay dose until resolved to ≤ Grade 1 or baseline level: If resolved in ≤7 days from day of onset, maintain dose If resolved in >7 days from day of onset, reduce dose 1 level
Grade 4	Discontinue patient from study treatment
Other Non-Laboratory Adverse Events	
Grade 3	Delay dose until resolved to ≤ Grade 1 or baseline: If resolved in ≤7 days from day of onset, maintain dose If resolved in >7 days from day of onset, reduce dose 1 level
Grade 4	Discontinue patient from study treatment

a There will be no dose modifications for Grade 1 to Grade 3 lymphopenia  
All dose modifications must be based on the worst preceding toxicity.  
CTCAE = Common Terminology Criteria for Adverse Events

*CONFIDENTIAL*

Sponsor/Innovations Study Numbers: DS6157-A-U101/GI 289

Study Drug: DS-6157a

Final Protocol: 17 August 2021 Version 6.0

